7.9.3 Compliance

Compliance will be described, by time of evaluation, by the number and percentage of subjects who filled out a questionnaire (per subject, at least one question answered) in that period of evaluation. The denominator used in calculating the percentage for baseline will be all randomized subjects. The denominator used for all other time points will be the number of subjects known to be alive at the start of the time period (**Table 62**).

7.9.4 Primary Analyses of QOL

The primary endpoints for the comparison of QOL between treatment arms will be proportions of patients who had deterioration in physical function and Global Health Status at 8 weeks and 16 weeks after the randomization. The deterioration is defined as a change score from baseline which is -10 points or lower [6]. Fisher's exact test will be used to compare the proportions of patients with deterioration between two treatment arms at these two time points (**Table 63**). No multiple adjustment for these comparisons will be made.

The proportions of patients who had improving (defined as change score from baseline of 10 points or higher) or stable (defined as change score from baseline of between -10 and 10 points) physical function and Global Health Status at 8 weeks and 16 weeks after the randomization will also be compared between two treatment arms using Fisher's exact test (**Table 63**).

The time to definitive deterioration in physical function and Global Health Status is defined as the time from randomization until the change score from baseline is -10 points or lower. For patients whose change scores are always higher than -10 points, the time to definitive deterioration will be censored at their last QoL assessment times. The log-rank test will be used to compare the time to definitive deterioration between two treatment arms (**Table 64**).

7.9.5 Baseline and Change Score Analysis

Descriptive statistics for EORTC QOL score (mean, standard deviation) will be presented for each scale at baseline. The same statistics will be generated at each time of post-baseline evaluation. The comparability of mean baseline scores and change scores at each time of post-baseline evaluation between treatment groups will be assessed using a Wilcoxon rank sum test (**Table 65** and **Table 66**).

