2.1 Study Design

Study CCTG CO.26 is a multi-centre, open-label, randomized phase II trial of durvalumab and tremelimumab combined with best supportive care *versus* best supportive care alone (where best supportive care is defined as those measures

designed to provide palliation of symptoms and improve quality of life as much as possible) in patients with refractory, advanced colorectal carcinoma. Patients are stratified by ECOG performance status (0 vs. 1) and site of tumour (right colon vs. transverse colon vs. left colon vs. rectum vs. unknown) prior to randomization. This study is conducted by CCTG with support from AstraZeneca. CCTG Case Report Forms (CRFs) are used and the database are maintained by CCTG.

A total of 180 patients would be enrolled (120 on Durva+Treme and 60 on BSC). The final analyses will be performed by CCTG when the required number of deaths (150) is recorded. This analysis plan describes the analyses performed at the completion of the study.

This study was activated on August 10, 2016 and closed to randomization of patients on June 29, 2017 after 180 patients were randomized. The CCTG Data Safety Monitoring Committee has been reviewing safety data every six months (usually at the time of the bi-annual CCTG Spring and Fall meetings) and as otherwise required. These analyses have been prepared by a CCTG/Queen's Senior Biostatistician.

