2.2 Treatment Allocation

The study is planned to randomize 180 subjects using a 2:1 allocation to durvalumab and tremelimumab combined with best supportive care (Durva+Treme Arm or ARM 2) and best supportive care alone (BSC Arm or ARM 1). The randomization was dynamically balanced by ECOG performance status (0 vs. 1) and site of tumour (right colon vs. transverse colon vs. left colon vs. rectum vs. unknown) using the method of minimization. A centralized system was used to randomize all patients in this study.

3. Objectives

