7.1 General Methods

All comparisons between treatment arms will be carried out using a two-sided test at an alpha level of 10% unless otherwise specified.

When appropriate, discrete variables are summarized with the number and proportion of subjects falling into each category, and compared using Fisher's exact test. Continuous and ordinal categorical variables are summarized using the mean, median, standard error, minimum and maximum values and when appropriate, compared using the Wilcoxon test. All confidence intervals are computed based on normal approximations except those for rates, which will be computed based on the exact method.

Time to event variables are summarized using Kaplan-Meier plots. Primary comparisons of the treatment groups are made using the stratified log-rank test. Primary estimates of the treatment differences are obtained with the hazard ratios and 90% confidence intervals from stratified Cox regression models using treatment arm as the single factor.

Percentages given in the summary tables will be rounded and may therefore not always add up to exactly 100%. Listings, tabulations, and statistical analyses will be carried out using the SAS (Statistical Analysis System, SAS Institute, North Carolina, USA) software.

Unless otherwise specified, date of randomization and stratification factors will be taken from the Centralized Randomization File.

Baseline evaluations will be those collected on Eligibility Checklist and Baseline Report and closest to, but no later than, the first day of study medication for treated subjects and closest to, but no later than, the date of randomization, for subjects who were randomized but who never received treatment.

Laboratory results, adverse events, and other symptoms are coded and graded using the Common Terminology Criteria for Adverse Events (CTCAE v4.0).

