7.9.2 Data Sets

The analyses of quality of life data will be restricted to randomized patients who have a measurement at baseline and at least one measurement after baseline.

The QOL assessment is performed prior to randomization and during chemotherapy/BSC at 4, 8, 16, and 24 weeks from randomization. Since exact time of assessment may vary from subject to subject, it is necessary to provide a window for each QOL time point. What follows is a description of how to assign a questionnaire to a discrete time point:

Time Point	Windows (i.e., time periods)
Baseline	14 days prior to up to the day of randomization
Week 4	2 weeks - < 6 weeks
Week 8	6 weeks - < 10 weeks
Week 12	10 weeks - < 14 weeks
Week 16	14 weeks - < 20 weeks
Week 24	20 weeks - < 28 weeks

If more than one questionnaire is available for the baseline window, then the latest non-missing measurement, per question, will be considered. If more than one questionnaire is available at a time point other than baseline, then the average (per question) of the non-missing measurements will be used.

Summary statistics, plots and longitudinal comparisons will be based on changes of the quality of life scores from baseline.

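### SAP 7.9.5 compares QLQ-C30 change scores by separate unadjusted Wilcoxon tests at each visit and reports no between-arm difference, so a supportive analysis is valid but less precise than it could be

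*SAP*

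**What the plan says.** SAP 7.9.5 sets the method, a two-sample rank test, in one sentence: "The comparability of mean baseline scores and change scores at each time of post-baseline evaluation between treatment groups will be assessed using a Wilcoxon". It names no covariate, stratum or model. Table 66 has a block for each of five visits (weeks 4, 8, 12, 16 and 24), giving N, mean and STD by arm and a p-value. It has no column for the difference between arms or its interval.

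SAP 7.9.2 adds: "Summary statistics, plots and longitudinal comparisons will be based on changes of the quality of life scores from baseline". No section of the SAP says what the longitudinal comparison is. The same section limits the analysis set to patients "restricted to randomized patients who have a measurement at baseline and at least one measurement after baseline", so a baseline assessment exists for everyone analysed.

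The Wilcoxon choice follows the default in SAP 7.1: "Continuous and ordinal categorical variables are summarized using the mean, median, standard error, minimum and maximum values and when appropriate, compared using the Wilcoxon test". On the factors used at allocation, SAP 2.2 says: "The randomization was dynamically balanced by ECOG performance status (0 vs. 1) and site of tumour". SAP 7.1 takes these factors from the randomization file. SAP 7.6.1, 7.6.3 and 7.6.5 use them for overall survival, progression-free survival and response, and Tables 33, 36 and 39 each show a treatment effect with a 90% interval.

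Quality of life is listed in Protocol 1.3 among the tertiary objectives. Its primary analysis is in SAP 7.9.4: Fisher's exact test on deterioration in physical function and global health status at weeks 8 and 16.

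**The concern.** Subtracting the baseline is one way of using it, but seldom the most efficient. When the correlation between baseline and follow-up is below 1, scores regress towards the mean. A change score therefore over-corrects for a chance baseline difference and varies more than a comparison in which the baseline slope is estimated. Leaving out ECOG and tumour site also departs from how the other efficacy endpoints are handled.

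Precision is limited here. The plan has "120 on Durva+Treme and 60 on BSC", and the design assumes a median survival of 4.5 months on best supportive care, so the control group answering questionnaires shrinks quickly. Each test uses only those who answered at that visit. A reader of a supportive-care comparison will want the size of any quality-of-life difference and its uncertainty, and Table 66 as laid out does not print either.

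**Working it through.** **The plan's own figure.** The documents give no sample size or power for quality of life. The only such figure is 150 deaths for overall survival (HR 0.65, 80% power, two-sided 10%, 2:1). It reproduces: (1.645 + 0.842)² / [(2/3)(1/3)(ln 0.65)²] = 6.18 / (0.2222 × 0.1856) = 149.9, rounded up to 150. This confirms the allocation and alpha reused below and says nothing about quality of life.

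**Inputs from the documents.** Allocation 120 to 60 (SAP 2.1); medians 4.5 and 6.9 months, HR 0.65 (Protocol 13.3); two-sided 10% (SAP 7.1); 10 points as a clinically relevant change (SAP 7.9.6).

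**Assumed, because the documents are silent.** Correlation r between baseline and follow-up, 0.3 to 0.8; common SD s (22 points in the illustration); 70% questionnaire completion among survivors; normally distributed scores.

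**Variance.** With the same SD s at both times, the per-patient variance of a change score is 2(1-r)s². After adjustment for baseline it is (1-r²)s². The ratio is (1-r)(1+r) / [2(1-r)] = (1+r)/2, a reduction of (1-r)/2. Interval width scales with the square root of the ratio.

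| r | change, 2(1-r) | adjusted, 1-r² | ratio | variance reduction | narrower interval, 1-√ratio |
|---|---|---|---|---|---|
| 0.3 | 1.40 | 0.91 | 0.65 | 35% | 19% |
| 0.5 | 1.00 | 0.75 | 0.75 | 25% | 13% |
| 0.7 | 0.60 | 0.51 | 0.85 | 15% | 8% |
| 0.8 | 0.40 | 0.36 | 0.90 | 10% | 5% |

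This compares means. Measured against the Wilcoxon test, whose efficiency relative to the t-test is 3/π under normality, the reductions become about 38%, 28%, 19% and 14%.

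**Illustration at week 8** (56/30.4375 = 1.84 months). Exponential survival at the design medians leaves 60 × exp(-ln 2 × 1.84/4.5) = 45 alive on best supportive care and 120 × exp(-ln 2 × 1.84 × 0.65/4.5) = 100 on the combination. At 70% completion, taking whole patients, that is 31 and 69. With SD 22 and a true difference of 10 points, 2,000 simulated trials at two-sided 10% gave this power:

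| r | Wilcoxon on change | baseline-adjusted (ANCOVA) |
|---|---|---|
| 0.3 | 56% | 72% |
| 0.5 | 64% | 76% |
| 0.7 | 83% | 90% |

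The 10 points in SAP 7.9.6 is a within-patient threshold, borrowed here as a between-arm difference. ECOG and tumour site are not in the simulation. Their association with the scores is not given, so their extra contribution cannot be computed.

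**The case against.** The case for leaving the plan alone has weight. The Wilcoxon test is the SAP's stated default, suits bounded and discrete scales, and remains valid for comparing the patients who answered. Section 7.9.5 supports a tertiary objective, and the primary quality-of-life tests in 7.9.4 would be the same after any change here. Table 66 gives N, mean and STD by arm, so an unadjusted difference and a normal-approximation interval could be worked out by hand. The size of the gain depends on r, and at 0.8 it is only 10%.

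All of that stands, and it limits the importance of the point. It does not answer two things. An adjusted estimate cannot be recovered from Table 66, and the longitudinal comparison mentioned in 7.9.2 remains undefined.

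Modelling has its own costs. A linear model on bounded scales is an approximation. A repeated-measures model assumes data are missing at random and implicitly carries a score for patients who have died. Five tumour-site levels may be sparse in the control arm, where about 26 of 60 would be alive at week 24 on the design median. Neither approach removes bias from death or non-completion.

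**Conclusion.** The point holds as one of efficiency and estimation. Under equal variances, baseline adjustment would cut the variance of the treatment difference by (1-r)/2, about 10% to 35% for an assumed r of 0.8 to 0.3. Bounded, discrete scores would alter these figures somewhat. The gain from ECOG and tumour site is plausible but cannot be quantified.

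Four stronger readings are tempting, and the documents do not support them:

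- **That the baseline score is thrown away.** It is subtracted, and it defines the analysis set. What is missing is its use as a covariate.
- **That the trial's conclusions are weakened.** Overall survival and the Fisher tests in 7.9.4 do not depend on 7.9.5.
- **That the number of tests (15 scales × 5 visits = 75) adds to the case.** An adjusted analysis yields the same number of contrasts, so it neither causes nor cures that problem.
- **That the baseline p-values in Table 65 are meaningless because of randomization.** The quality-of-life set is selected after randomization, by having a later questionnaire, in an open-label trial. Checking comparability in that set is reasonable.

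**What to change.** In SAP 7.9.5, for each scale, specify an estimate of the between-arm difference adjusted for baseline score, ECOG status and tumour site, with a stated rule for pooling sparse site levels. Two forms would serve:

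- analysis of covariance at each visit; or
- one repeated-measures model over weeks 4 to 24 with arm, visit, arm-by-visit, baseline and baseline-by-visit terms, a named covariance structure and a fallback if it does not converge. This form would also define the longitudinal comparison in 7.9.2.

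Add the adjusted difference and its 90% interval to Table 66, highlight weeks 8 and 16 to match 7.9.4, and keep the Wilcoxon tests as a sensitivity analysis. State the limits in the text: the linear approximation on bounded scales, the missing-at-random assumption if the repeated-measures form is used, and that the estimates do not correct for death or non-completion.

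The cost is SAP wording and programming. No new data are needed.

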7.9.6 QOL Response Analysis

QOL response for functional scales and global health status is calculated as follows: A change score of 10 points from baseline is defined as clinically relevant. Patients are considered to have clinical improvement if reporting a score 10-points or better than baseline at any time of QOL assessment. Conversely, patients are considered worsened if reporting a score minus 10-points or worse than baseline at any time of QOL assessment without any improvement. Patients whose scores are between 10-point changes from baseline at every QOL assessment will be considered as stable. In

contrast to functional scales, for the determination of patient’s QOL response, classification of patients into improved and worsened categories is reversed for symptom scales. A Chi-square test will then be performed to compare the distributions of these three categories between two arms (**Table 67**).

8. Appendices

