
* Table will be provided for each scale/domain/item.

** Wilcoxon rank sum test

Table 67: Results for QOL Response Analyses

Domain	DURVA+TREME			BSC			P-value*
	Improved	Stable N (%)	Worsened	Improved	Stable N (%)	Worsened	
EORTC QLQ-C30							
Physical	***(**)	***(**)	***(**)	***(**)	***(**)	***(**)	.**
Role	***(**)	***(**)	***(**)	***(**)	***(**)	***(**)	.**
Emotional	***(**)	***(**)	***(**)	***(**)	***(**)	***(**)	.**
Cognitive	***(**)	***(**)	***(**)	***(**)	***(**)	***(**)	.**
Social	***(**)	***(**)	***(**)	***(**)	***(**)	***(**)	.**
Global	***(**)	***(**)	***(**)	***(**)	***(**)	***(**)	.**
Pain	***(**)	***(**)	***(**)	***(**)	***(**)	***(**)	.**
Fatigue	***(**)	***(**)	***(**)	***(**)	***(**)	***(**)	.**
Nausea	***(**)	***(**)	***(**)	***(**)	***(**)	***(**)	.**
Dyspnea	***(**)	***(**)	***(**)	***(**)	***(**)	***(**)	.**
Sleep	***(**)	***(**)	***(**)	***(**)	***(**)	***(**)	.**
Appetite	***(**)	***(**)	***(**)	***(**)	***(**)	***(**)	.**
Constipation	***(**)	***(**)	***(**)	***(**)	***(**)	***(**)	.**
Diarrhea	***(**)	***(**)	***(**)	***(**)	***(**)	***(**)	.**
Financial	***(**)	***(**)	***(**)	***(**)	***(**)	***(**)	.**

* Chi-square test

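### The QoL response table compares ordered categories with an unordered chi-square; a stated ordinal test would answer the directional question with more power, at low priority

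*SAP*

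**What the plan says.** SAP 7.9.6 defines three classes from the change since baseline, with a 10-point threshold, and reports them in Table 67. On improvement: "Patients are considered to have clinical improvement if reporting a score 10-points or better than baseline at any time of QOL assessment". A patient counts as "worsened if reporting a score minus 10-points or worse than baseline at any time of QOL assessment without any improvement". The rest are stable. The comparison is: "A Chi-square test will then be performed to compare the distributions of these three categories between two arms". The Table 67 footnote agrees ("Chi-square test") and names no trend version. Table 67 has 15 rows: five functional scales, global health status and nine symptom scales.

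SAP 7.1 sets the general rules. For discrete variables: "discrete variables are summarized with the number and proportion of subjects falling into each category, and compared using Fisher's exact test" (the sentence opens with a when-appropriate qualifier). For ordered ones: "Continuous and ordinal categorical variables are summarized using the mean, median, standard error, minimum and maximum values and when appropriate, compared using the Wilcoxon test". Protocol 13.2 has no QoL analysis, so SAP 7.9.6 is the only place where this test is specified.

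**The concern.** Worsened, stable and improved are cut-points of a single change score, so they have a natural order. On a 2 × 3 table the Pearson chi-square has two degrees of freedom and treats the columns as mere labels. It follows neither general rule in SAP 7.1, and 7.9.6 does not say why.

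Two things are at stake. If the regimen shifts quality of life in one direction, part of the test's sensitivity is spent on patterns that nobody is asking about. And a small p-value does not say that quality of life is better or worse, because the test reacts just as readily when one arm has both more improvement and more worsening.

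There is also a smaller matter of classification. One rise of 10 points at any assessment outranks every decline, earlier or later, so the chance of being called improved grows with the number of forms a patient returns.

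**Working it through.** **Inputs from the documents.** Two-sided alpha 10% (SAP 7.1); 120 versus 60 randomized (SAP 2.1); QoL set limited to patients with a baseline and at least one later form (SAP 7.9.2), size not stated; median survival 4.5 and 6.9 months (Protocol 13.3); forms at weeks 4, 8, 12, 16 and 24, then every 12 weeks (Protocol 5.1, 5.2). No category rates, effect size or power are given for QoL, so those below are assumptions.

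**The plan's own power figure.** It concerns overall survival only. Schoenfeld events = (1.645 + 0.842)² / [(2/3)(1/3)(ln 0.65)²] = 6.18 / 0.0412 = 150, as stated.

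**Formulas.** Let h = n₂n₁/(n₂+n₁), d the Arm 2 minus BSC difference in each category, p̄ the pooled proportion, r the mid-cumulative pooled proportion (ridit), and v = Σp̄r² − 1/4.
- Chi-square: λ₂ = h Σ d²/p̄ on 2 df, critical value 4.605.
- Wilcoxon with midranks: λ₁ = h (Σ d·r)²/v on 1 df, critical value 2.706.

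**One-directional example.** Worsened/stable/improved 30/35/35% on Arm 2, 45/33/22% on BSC; 95 versus 42.
- h = 95×42/137 = 29.12; p̄ = 0.346, 0.344, 0.310.
- λ₂ = 29.12 × (0.0650 + 0.0012 + 0.0545) = 3.51.
- r = 0.173, 0.518, 0.845; Σd·r = 0.0943; v = 0.0740; λ₁ = 29.12 × 0.0943²/0.0740 = 3.50.

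Nearly all the signal is in the ordered direction, so the second degree of freedom is wasted.

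**Non-ordered example.** 45/20/35% against 40/35/25%; 120 versus 60.
- h = 40; p̄ = 0.433, 0.250, 0.317.
- λ₂ = 40 × (0.0058 + 0.0900 + 0.0316) = 5.09.
- r = 0.217, 0.558, 0.842; Σd·r = 0.01125; v = 0.0726; λ₁ = 0.07.

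Almost none of this signal is in the ordered direction.

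**Power at two-sided 10%, by simulation.** The formulas agree to within about 1 point.

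| Arm 2 vs BSC (worsened/stable/improved, %) | n | Chi-square | Wilcoxon |
|---|---|---|---|
| 30/35/35 vs 45/33/22 | 95/42 | 50% | 59% |
| 30/40/30 vs 40/40/20 | 95/42 | 33% | 40% |
| 45/20/35 vs 40/35/25 | 120/60 | 63% | 10% |
| 40/20/40 vs 40/35/25 | 120/60 | 72% | 28% |
| 25/50/25 vs 40/35/25 | 120/60 | 63% | 38% |

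Both tests reject about 10% of the time with no effect. Under proportional-odds shifts (common odds ratio 1.5 to 2.5, four assumed BSC distributions, 80/40 to 120/60 patients) the Wilcoxon gains about 5 to 10 points; at odds ratio 2.0 and 120/60 it is 65–68% against 75–77%. For a pure trend, 80% power on 1 df needs λ = 6.18 and on 2 df λ = 7.71, a ratio of 1.25. The chi-square then needs about 25% more patients, or has 71% power at the same size.

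**Any-time rule.** Assume no true change, global scale (steps of 100/12 = 8.33), mean 65, within-visit SD 10. The chance of being called improved on 1 to 5 forms is 19, 30, 37, 43 and 47% (14 to 37% at SD 8; 23 to 54% at SD 12). With 5 forms about 9% have both a rise and a fall of 10 points and are all called improved.

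For the gap between arms, take exponential survival S(t) = exp(−t ln 2/median) and assume every living patient returns each form. Forms per analysed patient = ΣS/S(week 4).
- BSC: (0.868 + 0.753 + 0.654 + 0.567 + 0.427)/0.868 = 3.8.
- Arm 2: (0.912 + 0.831 + 0.758 + 0.691 + 0.574)/0.912 = 4.1.

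Weighting the probabilities by the number of forms gives about 40% against 42% falsely improved, a gap of about 2 points through week 24. If forms to week 72 count, it is about 4 points.

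**The case against.** A reader might infer that 7.9.6 contradicts SAP 7.1. It does not. The Wilcoxon rule applies when appropriate, and 7.9.6 is the specific provision, with a matching table footnote. It is a departure without a stated reason.

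A reader might also infer that power is lost on all 15 scales. The documents give no rates or effect for any scale, and the loss depends on an ordered shift. A toxic but sometimes active regimen could empty the stable class in both directions, and there the chi-square is far stronger. So the change is not free. What remains of the concern in that case is interpretive: with more improvement and more worsening on Arm 2, a rejection shows that the distributions differ, not which arm did better. Table 67 does print the counts, so a reader can look for direction.

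The any-time rule invites a reading of serious bias. But 19% to 47% compares patients with one form and five, not the two arms; the gap between arms is about 2 to 4 points under the assumptions above. The form windows in SAP 7.9.2 stop at week 24, which favours the smaller figure, although 7.9.6 states no cut-off.

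Lack of stratification is not a fault particular to this table: the QoL tests in 7.9.4 and 7.9.5 are not described as stratified either.

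Finally, 7.9.5 already compares change scores on each scale at each visit by Wilcoxon, which answers much of the directional question. It does not replace the patient-level classification in Table 67.

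**Conclusion.** The point holds as an inexpensive improvement to a supportive table. SAP 7.9.6 uses an unordered test on ordered categories, departs from SAP 7.1 without explanation, and for a one-directional shift gives up about 5 to 10 points of power. That range rests on assumed category rates and analysis-set sizes; the plan supplies neither. It does not extend to shifts that are not ordered, where the ranking of the two tests reverses.

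The any-time classification is a minor note, worth about 2 points between arms through week 24 and about 4 to week 72, with no true change and SD 10 assumed.

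Priority is low. QoL is a tertiary objective (Protocol 1.3), and the primary QoL analysis is the proportion deteriorating at weeks 8 and 16 (SAP 7.9.4).

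**What to change.** In SAP 7.9.6 and the Table 67 footnote, name the Wilcoxon rank-sum test on worsened < stable < improved (equivalently a Cochran-Mantel-Haenszel row-mean-score test with rank scores) as the test, and keep the chi-square as supportive. If the chi-square is to stay as the main test, state why. Adjusting for the randomization factors is optional. Make the edit before QoL data are compared by arm.

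The cost is one sentence, one footnote and a change of procedure option, with no new data. The statistical price is lower power for shifts out of stable in both directions or between two adjacent categories only; the supportive chi-square would still show these.

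Optionally, limit the classification to forms up to a common assessment, such as week 24. That removes the growth of the gap from later forms, though not all dependence on the number returned. Requiring the change on two consecutive forms is not recommended as a remedy: a patient with a single form could never qualify, so the result would still depend on how many forms were returned. Using the last form would compare patients at different times.
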